## Protocol Amendment Summary of Changes Table

DOCUMENT HISTORY	
Protocol Version	Protocol Version Date
Protocol Amendment C	21 Mar 2025
Protocol Amendment B	06 Feb 2024
Protocol Amendment A	26 Jul 2021
Original Protocol	01 Nov 2017

### Amendment C [21 Mar 2025]

This amendment is considered to be nonsubstantial based on the criteria set forth in Regulation (EU) No 536/2014 of the European Parliament.

### Overall Rationale for Amendment C:

To align the endpoints throughout the protocol in the three sections where they are listed: Summary of Protocol Section: Synopsis, Trial Objectives: Section 5.2, Statistical Methods: Section 11.2. To clarify the trial imaging assessments collection timepoints and the timepoints that were analyzed by the independent reading center (RC).

Additional administrative updates and clarifications were also made, prior to unmasking of the study. Refer to the table below for the description and brief rationale for each change.

Section # and Name	Description of Change	Brief Rationale

 
• Section 2 Summary of Protocol OPH2005: Synopsis Table Endpoints
 
• Section 5.2: Endpoints
 
	
Adjusted wording of endpoint descriptions:
 
 
• For applicable endpoints, revised description to delete “over 18 months”.
 
• For endpoints of rate of change, revised description to use “through Month 18”.
 
• For endpoints of change from baseline, revised description to use “at Month 18”.
 
 
Secondary and supportive endpoints were split under separate headings.
 
Removed “mean” from applicable endpoint descriptions.
	
For clarity and consistency in endpoint presentation throughout the protocol.

 
• Section 2 Summary of Protocol OPH2005: Synopsis Table Endpoints
 
• Section 5.2: Endpoints
 
	
Removed “at the position of maximum width of ellipsoid zone loss” from the applicable supportive endpoint.
	
Following the internal sponsor review and discussions with the RC, it was decided that the secondary endpoint of outer nuclear layer (ONL) alignment will now be analyzed through the foveal center instead of at the position of maximum ellipsoid zone loss. Measuring the maximal ONL thickness through the fovea center in the same B-scan is more accurate, as the position of the maximum width of the ellipsoid zone loss can vary over time. This variability can cause inconsistencies. Therefore, ONL measurements will be conducted through the foveal center to ensure consistency.


 
• Section 2 Summary of Protocol OPH2005: Synopsis Table Endpoints
 
• Section 5.2: Endpoints
 
	
Removed secondary endpoint: Mean rate of change in the horizontal width of undetectable ellipsoid zone measured by a horizontal scan through the foveal center with SD-OCT over 18 months.
	
The primary endpoint captures the overall ellipsoid zone area defect. Measuring the area is more effective than measuring the width, as ellipsoid zone width can vary between adjacent scans and with degeneration of ellipsoid zone. Measuring one scan can also yield variability; as

Section # and Name	Description of Change	Brief Rationale
		
disease progresses, you may capture areas of degeneration of the ellipsoid zone versus areas of absent ellipsoid zone.
 
Area measurement takes into account multiple scans, providing a more consistent assessment.
 
The initial inclusion of this secondary endpoint was included as a potential practical clinical surrogate of the ellipsoid zone defect using one measurement (one number) versus area, which requires a calculation.

Section 3: Schedule of Assessments	Superscripted footnote #7 added to Microperimetry Testing row in the continued portion of the table.	For consistency and clarity in presentation of this optional assessment.
Section 7: Procedures	Added text under section heading: Imaging assessments are collected at the timepoints specified in Section 10.2 “Trial Assessments”. The RC will analyze the data from three timepoints prior to database lock: Screening, Month 9 and Month 18. The additional imaging assessments collected at Month 3, Month 6, Month 12 and Month 15 will be stored and made available if needed.	To clarify which timepoints will be analyzed by the RC.
Section 11.2: Endpoints	Removed endpoint details from the section and added cross-reference to Section 5.2.	For document conciseness.
Section 11.3: Study Design	Revised study design description as follows: This is a randomized, double masked, Sham controlled, Phase 2b trial that will obtain evidence regarding the effect of avacincaptad pegol on the <del>mean</del> rate of change in the area of ellipsoid zone defect ( defined as ellipsoid zone attenuation in addition to total RPE loss ) measured by en face SD-OCT <del>over</del>	For consistency with the change to the description of the primary endpoint and to provide clarity and accuracy to the meaning of ellipsoid zone defect.

Section # and Name	Description of Change	Brief Rationale
	
from Baseline through Month 18, when compared with Sham.
	

Section 11.4.3: Statistical Analyses
	
Revised primary endpoint analysis description as follows:  Primary endpoint will be analyzed using a mixed model for repeated measures (MMRM) with all available data, using response variable of the area of ellipsoid zone defect measured by en face SD-OCT over time up to Month 18 including baseline and post-baseline assessments. The MMRM will be used to assess the difference between the treatment groups in terms of the rate of change (slope) <del>of</del> in the area of ellipsoid zone defect from Baseline through Month 18 over time of 18 months. <del>For the model, The</del> fixed effects will include treatment group (avacincaptad pegol or Sham), time, pooled geographic region (North America or Rest of World) and treatment by time interaction.
	
 
• To clarify for readability.
 
• To parsimoniously adjust for the randomization stratification factor “Site” in the analysis.
 

Section 11.4.3: Statistical Analyses
	
Revised efficacy analysis population as follows:  The efficacy analysis will be conducted on all randomized <del>and treated</del> subjects according to the intention-to-treat principle.
	
To clarify that all randomized patients, irrespective of whether they were treated with study drug, will be included in the analysis, following the intention-to-treat principle.

Entire document
	
Administrative updates.
	
To provide updated information and clarification throughout the protocol.

## 1. GLOSSARY OF ABBREVIATIONS

A2E	N-Retinylidene-N-Retinyethanolamine
AAV	Adeno Associated Virus
ABC	ATP-Binding Cassette
AE	Adverse Event
atRal	All- Trans -Retinal
ALT	Alanine Aminotransferase
AMD	Age-Related Macular Degeneration
AST	Aspartate Aminotransferase
ATP	Adenosine Triphosphate
BCVA	Best corrected visual acuity
Bsl	Baseline
BUN	Blood Urea Nitrogen
CFH	Complement Factor H
CLIA	Clinical Laboratory Improvement Amendments
CRF	Case Report Form
CRO	Contract Research Organization
CRRY	Complement Receptor 1-Like Protein Y
DDAF	Definite Decrease in Autofluorescence
DNA	Deoxyribonucleic Acid
DSMB	Data Safety Monitoring Committee
EC	Ethics Committee
ECG	Electrocardiogram
ETDRS	Early Treatment Diabetic Retinopathy Study
EW	Early Withdrawal
FA	Fluorescein Angiography
FAF	Fundus Autofluorescence
FDA	Food and Drug Administration
FE	Fellow Eye
FP	Color Fundus Photography
GA	Geographic Atrophy
GCP	Good Clinical Practice
GGT	Gamma-Glutamyl Transferase
HbA1c	Hemoglobin A1c
hERG	Human Ether-a-go-go-Related Gene
HRA	High resolution angiography
IB	Investigator's Brochure
ICH	International Council for Harmonisation of Technical Requirements for Pharmaceuticals for Human Use
IFU	Instructions for Use
IND	Investigational New Drug
INN	International non-proprietary name

IOP	Intraocular Pressure
IPCV	Idiopathic Polypoidal Choroidal Vasculopathy
IRB	Institutional Review Board
IRT	Interactive Randomization Technology
MAC	Membrane Attack Complex
MMRM	Mixed model for repeated measures
NLP	No Light Perception
NVAMD	Neovascular Age-Related Macular Degeneration
NYHA	New York Heart Association
OCT	Optical Coherence Tomography
OGTT	Oral glucose tolerance test
ONL	Outer Nuclear Layer
OU	Both Eyes
PEG	Polyethylene Glycol
RC	Reading Center
RNA	Ribonucleic Acid
RPE	Retinal Pigment Epithelium
SAE	Serious Adverse Event
SAP	Statistical Analysis Plan
Scr	Screening
SD-OCT	Spectral Domain-Optical Coherence Tomography
SE	Study Eye
SGOT	Serum Glutamic Oxaloacetic Transaminase
SGPT	Serum Glutamic Pyruvic Transaminase
SOP	Standard operating procedure
STGD	Stargardt Disease
STGD1	Stargardt Disease 1
WBC	White Blood Cell

## 2. SUMMARY OF PROTOCOL OPH2005

SYNOPSIS	
TITLE:	A Phase 2b Randomized, Double-masked, Controlled Trial to Establish the Safety and Efficacy of Zimura™ (Complement C5 Inhibitor) Compared to Sham in Subjects with Autosomal Recessive Stargardt Disease
OBJECTIVES:	The objectives of this study are to evaluate the safety and efficacy of avacincaptad pegol intravitreal injection compared to Sham in subjects with autosomal recessive Stargardt disease 1 (STGD1).
STUDY DESIGN:	
Subjects will be randomized in a 1:1 ratio to the following dose groups:
 
 
• Avacincaptad pegol (Zimura™)
 
• Sham
 
 
Note: The international non-proprietary name [INN] of the investigational product, Zimura™, is avacincaptad pegol.
 
All subjects will be treated as follows:
 
Induction Phase: Administered on Day 1, Month 1, and Month 2 in the following sequence, 14 days apart:
 
 
• D0: Avacincaptad pegol 2 mg/eye or Sham
 
• D14: Avacincaptad pegol 2 mg/eye or Sham
 
 
Maintenance Phase: Administered monthly (Month 3 – Month 17):
 
 
• Avacincaptad pegol 4 mg/eye (administered as two injections of avacincaptad pegol 2 mg)
 
• Sham + Sham
 
 
Monthly doses should be targeted for every 30 days from the last monthly visit and must be administered at least 21 days apart. There will be a final follow-up visit for all subjects at Month 18.

ENDPOINTS:	
Primary Efficacy Endpoint
 
 
• Rate of change in the area of ellipsoid zone defect measured by en face spectral domain-optical coherence tomography (SD-OCT) from Baseline through Month 18.
 
 
Secondary Endpoints
 
 
• Change in best corrected visual acuity (Early Treatment Diabetic Retinopathy Study [ETDRS] letters) from Baseline at Month 18.
 
• Change in photopic and/or mesopic macular sensitivity measured by microperimetry (optional assessment) from Baseline at Month 18.
 
 
Supportive Endpoints
 
 
• Rate of change in the area of atrophic lesion (definite decrease in autofluorescence, DDAF) measured by fundus autofluorescence (FAF) from Baseline through Month 18.
 
• Rate of change in the thickness of the outer nuclear layer
 

SYNOPSIS	
	
(ONL) measured by a horizontal scan through the foveal center using SD-OCT from Baseline through Month 18.
 
 
• Time to persistent vision loss (defined as BCVA loss <math>\geq</math> 10, 15 or 20 letters from Baseline at two or more consecutive visits through Month 18).
 
• Emergence of at least one new atrophic lesion (DDAF) measured by FAF through Month 18.
 
 
Safety Endpoints:
 
 
• Adverse events, vital signs, ophthalmic variables [ophthalmic examination, intraocular pressure (IOP), fluorescein angiogram (FA), FAF, SD-OCT, microperimetry], ECG and laboratory variables.
 

PLANNED SAMPLE SIZE:	Approximately 120 subjects will be enrolled in this study, 60 per dose group.
SUBJECT SELECTION:	Subjects of either gender, aged 18 – 60 years of age (inclusive), with the diagnosis of STGD1.
TEST DRUG DOSAGE:	Subjects randomized to avacincaptad pegol will receive 6 doses of avacincaptad pegol 2 mg and 15 doses of avacincaptad pegol 4 mg.
FORMULATION AND PRESENTATION:	
Formulation
 
Avacincaptad pegol is formulated at a concentration of 20 mg/mL (oligonucleotide mass) in 10 mM phosphate buffered saline at pH 6.8-7.8 as a sterile aqueous solution. The drug product is preservative-free and intended for intravitreal injection only. The drug product should not be used if cloudy or if particles are present.
 
Presentation
 
The clinical supply kits contain either an avacincaptad pegol standard 2R vial [Schott] or an empty 2R vial, along with BD syringe and BD filter needle.
 
The drug product was originally presented in a USP Type I high recovery glass vial that contained a 0.5 mL v-shaped well sealed with FluoroTec®-coated, halobutyl rubber stoppers and red aluminum crimp seals. In March 2023, the drug product was transitioned to presentation in a 2 mL (ISO 2R) Type I glass vial, stoppered with FluoroTec-coated, halobutyl rubber stopper, and sealed with aluminum crimp seals.
 
Instructions for Use (IFU) are provided directly to the study site.
 
Dosing Information
 
The avacincaptad pegol 2 mg/eye dose will be administered in a total injection volume of 0.1 mL (100 <math>\mu</math>L). Avacincaptad pegol 4 mg/eye will be administered as two 0.1 mL (100 <math>\mu</math>L) injections.
 
Comparator Sham Procedure
 
To preserve the randomized treatment arm masking, subjects will have the sham procedure performed at study treatment visits.

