#### **Ophthalmic Inclusion Criteria**

The following inclusion criteria apply to the study eye:

- 8.2.1 At least two pathogenic mutations of *ABCA4* gene confirmed by a CLIA-certified laboratory.
- 8.2.2 Best corrected visual acuity in the study eye between 20/20 - 20/200 Snellen equivalent, inclusive.
- 8.2.3 Presence of at least one identifiable location of at least 250 micrometers contiguous width of ellipsoid zone loss on SD-OCT within the total 9 ETDRS subfields.
- 8.2.4 The total area of thinned layer(s) on OCT not extending beyond the outer ring of the total 9 ETDRS subfields (e.g., not extending beyond fields 5-9).
- 8.2.5 Fundus autofluorescence may show heterogeneous signals (areas of increased and/or decreased autofluorescence) but no area of subfoveal definitely decreased autofluorescence (DDAF).
- 8.2.6 Clear ocular media and adequate pupillary dilatation in both eyes (OU) to allow for all imaging procedures, including good quality stereoscopic fundus photography, fundus autofluorescence, and spectral domain ocular coherence tomography.
- 8.2.7 Intraocular pressure of 21 mmHg or less in the study eye.

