4.2.3 Demographic and Other Baseline Characteristics

Demographics and other baseline characteristics will be summarized descriptively by treatment group and overall, for the ITT population.

The variables to be summarized are:

- Gender, ethnicity, race, age, age group (18 to <65 years, >=65 years), current smoking status, iris color, study eye, height, weight, intraocular pressure (study/fellow eye)
- FAF imaging assessments for study eye
- BCVA (ETDRS letters) for study/fellow eye
- Ophthalmic exam for study/fellow eye (motility, lids/lacrimal/lashes, conjunctiva/sclera, cornea, anterior chamber activity: cells, iris, pupils, lens status, vitreous haze, vitreous hemorrhage, posterior vitreous detachment, optic nerve, macula, retinal vessels, peripheral retina)

Prior ocular history as coded by MedDRA for study eye and fellow eye will be summarized by Preferred Term (PT), by treatment group and overall, in the SAF population.

Medical history as coded by MedDRA (excluding ocular history) will be summarized by System Organ Class (SOC) and PT, by treatment group and overall, in the SAF population.

Prior surgeries/procedures as coded by MedDRA will be summarized by SOC and PT, by treatment group and overall, in the SAF population.

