Time to persistent vision loss is defined for each participant as the first study day (in months) where the participant experiences a BCVA loss ≥ 10 , 15 or 20 letters from Baseline at two or more consecutive visits through Month 18. Participants without a vision loss event have their time to event censored at the last assessment of BCVA prior to the end of the study, or at 0.03285 months (i.e. day 1) if no post-baseline BCVA assessments are available. The hazard ratio for ACP vs. Sham on time to persistent vision loss, along with its corresponding 95% CI, will be calculated using a stratified Cox proportional hazards regression model with

pooled geographic region (North America or Rest of World) as the stratification factor. The two-sided p-value will be derived using the stratified log-rank test with pooled geographic region as the stratification factor. The 5th percentile and median time to the first occurrence of persistent vision loss will be analysed using the Kaplan-Meier method without stratification. Additionally, the event rate at Month 6, 9, 12, 15 and 18, and corresponding 95% CIs will be estimated using the Kaplan-Meier method without stratification and Greenwood formula with complementary log-log transformation.

For the emergence of at least one new atrophic lesion (DDAF) through Month 18, participants who do not have any atrophic lesion (DDAF) assessments through Month 18 will be excluded from the analysis. A dichotomized response (yes or no new atrophic lesion) will be evaluated and tested using Cochran-Mantel-Haenszel χ^2 test for risk difference between ACP and Sham adjusting for the stratification factor of pooled geographic region (North America or Rest of World). The odds ratio and its corresponding 95% CI will be reported for ACP vs. Sham.

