5 SUPPORTING DOCUMENTATION

5.1 Appendix 1 Randomization Approach

The dynamic minimization algorithm described in Pocock and Simon (Pocock et al. 1975) was used to allocate patients to either ACP or Sham in this study. This procedure consists of two steps. First, the level of balance in treatment assignments within 1) the strata of randomization stratification factors (i.e. site) and 2) the overall population are determined for the settings where a new participant is assigned to ACP or Sham. Then, the treatment assignment that would cause the least imbalance is attributed higher probability when assigning the actual treatment assignment to the new participant. Note that this allocation scheme helps balance the treatment assignment while maintaining a random component.

Imbalance measures

Let X_{jk} be the number of participants already assigned to treatment k ($k = \text{ACP, Sham}$) within site j ($j = 1, 2, \dots, S$) as the new participant to be assigned. That is, X_{jACP} and X_{jSham} are the number of participants already assigned to receive ACP and Sham within site j , respectively. Additionally, let Y_{ACP} and Y_{Sham} be the total number of participants already assigned to ACP and Sham across all sites, respectively.

Suppose a new participant is enrolled at Site j . Then, the imbalance in treatment assignments at the site-level is defined by:

$$D_{ACP} = |X_{jACP} - X_{jSham} + 1| \text{ if the new participant is assigned to ACP or}$$

$$D_{Sham} = |X_{jACP} - X_{jSham} - 1| \text{ if the new participant is assigned to Sham}$$

Where $|a|$ is the absolute value of a . Similarly, the imbalance in treatment assignments in the overall population is defined by:

$$T_{ACP} = |Y_{ACP} - Y_{Sham} + 1| \text{ if the new participant is assigned to ACP or}$$

$$T_{Sham} = |Y_{ACP} - Y_{Sham} - 1| \text{ if the new participant is assigned to Sham}$$

The overall imbalance measure is defined by:

$$I_t = W_1 D_t + W_2 T_t \text{ (} t = \text{ACP or Sham)}$$

Where W_1 and W_2 are positive weights that sum to one and are prespecified before the second participant has been randomized. The weights will only be made available to the broader study team after database lock.

Allocation

The first participant will be assigned to ACP or Sham with equal chance. Then, for each subsequent participant, the participant will be assigned to ACP with probability p or to Sham with probability $1 - p$, based on the following rules:

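### The test for new atrophic lesions adjusts only for region although eyes with and without baseline DDAF can enter; it is valid, but may give up power and is exposed to chance imbalance

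*Protocol*

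**What the plan says.** The protocol synopsis and Section 5.2 list, among the supportive endpoints, "Emergence of at least one new atrophic lesion (DDAF) measured by FAF through Month 18". SAP 4.5 turns this into a binary outcome: "A dichotomized response (yes or no new atrophic lesion) will be evaluated and tested", by a CMH "test for risk difference between ACP and Sham adjusting for the stratification factor of pooled geographic region (North America or Rest of World"). An odds ratio with a 95% confidence interval is to be reported as well; the SAP does not say whether it is stratified. The only participants left out are those with no DDAF assessment through Month 18. No sensitivity or supplementary analysis is planned for this endpoint.

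On who can enter, criterion 8.2.5 reads: "Fundus autofluorescence may show heterogeneous signals (areas of increased and/or decreased autofluorescence) but no area of subfoveal definitely decreased autofluorescence (DDAF"). On allocation, SAP Appendix 1 describes minimization on balance within "the strata of randomization stratification factors (i.e. site") and in the overall population. Baseline DDAF is not a factor.

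The baseline information exists. FAF is done at Screening (Protocol 10.2.1), the reading center analyzes the Screening images (Protocol Section 7), and SAP 4.2.3 summarizes "FAF imaging assessments for study eye" at baseline.

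**The concern.** The criterion admits two kinds of eye. In an eye without DDAF at Screening, a new lesion is the first one seen. In an eye with extrafoveal DDAF, it is an additional one. The endpoint scores both as the same event, and neither document separates them.

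If the two kinds of eye develop new lesions at different rates, baseline DDAF is a prognostic factor that neither the allocation nor the test takes into account. Two things follow. Between-eye variation that could be removed stays in the comparison. And if the arms of this one trial happen to differ in baseline DDAF, the estimated risk difference moves in a direction that could be foreseen from the baseline table. The plan already handles this elsewhere: SAP 4.4.2 adjusts both secondary endpoints for their baseline value.

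**Working it through.** **Inputs from the documents.** About 120 subjects, 60 per arm (Protocol synopsis); two-sided 5% level (SAP 4.1); region as the only stratum (SAP 4.5). No event rate, power or sample size is stated for this endpoint. The arm size agrees with the plan's own threshold for the primary endpoint: 1.96 × √(2/60) = 0.3578, against the stated 0.3577 (Protocol 11.3.1).

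**Assumptions.** The prevalence q of baseline DDAF, and the 18-month new-lesion risks r1 (with) and r0 (without). The documents give none of these.

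**Step 1: chance imbalance.** The SD of the between-arm difference in prevalence is √(2q(1−q)/60). At q = 0.5 this is √(0.5/60) = 9.1 percentage points; at q = 0.3 or 0.7 it is 8.4 points. This treats allocation as independent of baseline DDAF.

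**Step 2: effect on the risk difference.** With m = q·r1 + (1−q)·r0 and no treatment effect:
- unadjusted SE = √(2m(1−m)/60)
- shift for a 1-SD imbalance = imbalance SD × (r1 − r0)
- variance ratio, stratified to unadjusted = [q·r1(1−r1) + (1−q)·r0(1−r0)] / [m(1−m)]

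For q = 0.5:

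| r1 vs r0 | Unadjusted SE (points) | Shift for 1 SD (points) | Variance ratio | Variance removed |
|---|---|---|---|---|
| 30% vs 20% | 7.9 | 0.9 | 0.1850/0.1875 = 0.987 | 1% |
| 40% vs 15% | 8.2 | 2.3 | 0.18375/0.199375 = 0.922 | 8% |
| 50% vs 10% | 8.4 | 3.7 | 0.170/0.210 = 0.810 | 19% |
| 60% vs 10% | 8.7 | 4.6 | 0.165/0.2275 = 0.725 | 27% |

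**Step 3: type I error given the imbalance.** Take q = 0.5 and 50% vs 10%. The unadjusted test rejects beyond 1.96 × 8.37 = 16.4 points, while the spread at a fixed imbalance is √(2 × 0.170/60) = 7.5 points. With perfect balance the error is 0.029. At the 95% limit of imbalance (1.96 × 9.1 = 17.9 points) the shift is 17.9 × 0.4 = 7.2 points and the error is 0.11. Over q from 0.3 to 0.7 and risk gaps from 20 to 50 points, the error at that limit is about 0.06 to 0.14.

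**Step 4: simulation.** 10,000 trials, simple 60:60 allocation (not the plan's minimization), half the participants in each region, q = 0.5, risks 50% vs 10%:

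| | CMH by region | CMH by region and DDAF |
|---|---|---|
| Type I error, all trials | 0.050 | 0.048 |
| Type I error, imbalance ≥ 15 points (10% of trials) | 0.124 | 0.053 |
| Power if treatment halves both risks | 0.51 | 0.56 |

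**Step 5: the odds ratio.** In the scenarios of Step 2, the unstratified variance of the log odds ratio is 1/[30·m(1−m)]. Stratified by DDAF it is 1/{15·[r1(1−r1) + r0(1−r0)]}, which is larger by the reciprocal of the variance ratio. The SE on the log scale rises by √(1/0.922) − 1 = 4%, √(1/0.810) − 1 = 11% and √(1/0.725) − 1 = 17% for the last three rows of the first table.

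**The case against.** The strongest reply is that nothing is broken. Randomization covers chance imbalance, and the shift is already part of the unadjusted SE rather than an addition to it: for 40% vs 15%, √(7.83² + 2.28²) = 8.15 points. Having at least one new lesion is a single definition applied alike to both arms. The documents do not say that baseline DDAF predicts new lesions; if it does not, there is no systematic shift. Even in a favorable assumed case the power gain is about 5 points. All of this stands, and it limits the point to precision and conditional behavior.

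It is also true that the baseline FAF summary could reveal an imbalance. That would come only after unmasking, when any adjustment would be post hoc.

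A reader might infer four stronger claims, which the documents do not support:
- **That the test is invalid.** Its overall type I error is about 0.05.
- **That the reported confidence interval is wider than necessary.** The only interval specified for this endpoint is for the odds ratio. Stratifying would widen it on the log scale (Step 5), even though the test can gain power.
- **That the endpoint feeds the three-category decision.** In Protocol 11.3.1 the cut-offs depend only on the primary slope difference. Supportive endpoints enter a broader assessment around them, and this one is outside the fixed sequence in SAP 2.1.
- **That the Cox model for persistent vision loss has the same fault because it omits baseline BCVA.** That event is loss from each participant's own baseline, and no size has been worked out. Its p-value comes from a stratified log-rank test, which a Cox covariate would not change.

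**Conclusion.** The point holds as a minor improvement. The planned analysis is valid, but it leaves unused a baseline factor that eligibility allows to vary and that is available from Screening images. If that factor is prognostic, the plan loses some power and has no prespecified protection against a chance imbalance in the trial actually run. At 50% prevalence and 60 per arm, the gain runs from negligible (1% of the variance) to useful (27%). Where it falls in that range depends on prevalence and lesion risks that the documents do not give.

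Separately, and even with perfect balance, a single pooled result cannot show whether a treatment difference concerns first lesions, additional lesions or both.

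**What to change.** In SAP 4.5, before unmasking:
- Stratify the CMH test for the risk difference by pooled region and baseline DDAF (present or absent at Screening).
- Tabulate events by arm within each baseline DDAF stratum, so that first and additional lesions can be seen separately.
- State whether the odds ratio is stratified by baseline DDAF. If it is, say that it becomes conditional on baseline DDAF and that its interval may widen on the log scale.

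The cost is a few sentences and one table; no new data are needed. The other drawback is four strata instead of two. If region and DDAF each split participants evenly, that averages 60/4 = 15 per arm in each stratum.
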